Table 2 Study Drug Starting Dose by Age Cohorta in the Core Phase and Extension Phase

Age Range (Years)	Study Drug Starting Dose (mg)	Formulation
	Cohort 1	
≥12 to <18 20 mg Once Daily Oral Tablet		
Cohort 2		
≥6 to <12	20 mg Once Daily	Oral Tablet
Cohort 3		
≥1 to <6	10 mg Once Daily	Capsule

a: Subject age at the time of randomization will be used. The starting dose of study drug may be revised after scheduled PK/PD and safety reviews (Section 5.1).

Table 3 Study Drug Dose Adjustments in the Core Phase and Extension Phase

Platelet Count (×10 ⁹ /L)	Dose Adjustment or Action
$<50\times10^9/L$ after at least 2 weeks of dosing.	 Increase 1 Dose Level per Table 4. Wait 2 weeks to assess the effects of this regimen and any subsequent dose adjustments.
>150×10 ⁹ /L to ≤250×10 ⁹ /L	 Decrease 1 Dose Level per Table 4. Wait 2 weeks to assess the effects of this regimen and any subsequent dose adjustments.
>250 ×10 ⁹ /L	 Stop study drug. Increase platelet monitoring to twice weekly. When platelet count is ≤100×10⁹/L, decrease 1 Dose Level per Table 4.
<30×10 ⁹ /L after 3 weeks of once daily dosing at the cohort defined maximum dose per Table 4.	Discontinue study drug.
Also see protocol stopping criteria in Section 5.3 and early termination criteria in Section 6.1.6.	
>250×10 ⁹ /L after 2 weeks of once weekly dosing for any age cohort	Discontinue study drug.

 Table 4
 Study Drug Dose Level Titration (Core and Extension)

Dose	Dose Level
Cohort 1 (≥12 to <18 Years) and Cohort 2 (≥6 to <12 Years) Dosed with Oral Tablet	
40 mg Once Daily	6
40 mg Three Times a Week AND 20 mg on the Four Remaining Days of Each Week	5
20 mg Once Daily ^a	4
20 mg Three Times a Week	3
20 mg Twice a Week	2
20 mg Once Weekly	1
Cohort 3 (≥1 to <6 Years) Dosed with Powder for Oral Suspension	
20 mg Once Daily	6
20 mg Three Times a Week AND 10 mg on the Four Remaining Days of Each Week	5
10 mg Once Daily ^a	4
10 mg Three Times a Week	3
10 mg Twice a Week	2
10 mg Once Weekly	1

a: Subject age at the time of randomization will be used. Initial dose regimen based on modeling and simulation. Actual initial dose in Cohort 2 and Cohort 3 may be modified after modeling is completed using data from the previous cohort.

To ensure accuracy of the predictions, PK, platelet response, and safety data will be reviewed by the Sponsor, or the Sponsor's unblinded designee, as described in Section 5.1 and if necessary, adjustments of the dose level may be made following these data reviews.

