1.5.4 Extension Phase Dosing Regimen

Subjects who complete the 12 week Core Phase of the study, or who meet the stopping criteria as defined in Section 5.3 and are discontinued from the Core Phase, will be eligible to enter the open-label Extension Phase, if they continue to meet the inclusion criteria and do not meet any exclusion criteria for this phase of the study (Section 4.1.2).

In the Extension Phase of the study, subjects will receive open-label avatrombopag as either the film-coated oral tablet (20 mg per tablet) or as a capsule containing a powder for oral suspension (10 mg per capsule) which can be opened to sprinkle the contents into an appropriate vehicle. The formulation received should be recorded in the electronic case report form (eCRF). The appropriate Extension Phase starting dose of open-label avatrombopag should be determined based on the instructions below.

- If a subject entering the Extension Phase has a platelet count within the target range of ≥50×10⁹/L to ≤150×10⁹/L on their current dose of study drug, they may continue that dose of open-label avatrombopag when entering the Extension Phase.
- If a subject entering the Extension Phase has a platelet count <50×10⁹/L when entering the Extension Phase, the subject should be started on the dose of open-label avatrombopag listed in Table 2, based on the subject's age cohort.
- If a subject entering the Extension Phase has a platelet count >150×10⁹/L when entering the Extension Phase, the initial dose of open-label avatrombopag in the Extension Phase should be titrated down per the instructions in Table 4, based on the subject's platelet count, in order to maintain a platelet count between ≥50 to ≤150×10⁹/L.

Throughout the Extension Phase, the dose of open-label avatrombopag may be titrated up or down per the instructions in Table 4, based on the subject's platelet count, in order to maintain a platelet count between >50 to $<150\times10^9/L$.

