4.1.2 Extension Phase

Subjects who complete the 12 week Core Phase of the study, or who meet the stopping criteria as defined in Section 5.3 and are discontinued from the Core Phase, will be eligible to enter the open-label Extension Phase, if they continue to meet the inclusion criteria and do not meet any exclusion criteria for this phase of the study. Subjects and/or the subject's LAR must complete informed consent/assent in order to participate in the Extension Phase of the study.

Until the last subject completes the Core Phase and the database is locked, the Sponsor, all subjects, and all Investigators will remain blinded to treatment received in the Core Phase. Dosing of openlabel avatrombopag during the Extension Phase is described in Section 1.1.6.

Study visits will begin with Visit E-1/Month 1 which will be the same day as Visit 14 in the Core Phase. After dosing with open-label avatrombopag has been initiated during Visit E-1/Day 1, the subject should have weekly platelet counts drawn until it is determined that the subject is receiving a stable dose of avatrombopag. Otherwise, during the Extension Phase, visits will occur every 30 days for 24 months through Visit E-24/Month 24 (Figure 4).

Figure 4 AVA-PED-301: Extension Phase Study Schematic

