9.1.14 Visit 13 (Week 11; Day 78 ± 1 Day)

The following assessments will be performed during Visit 13:

- Perform WHO Bleeding Scale Assessment (Appendix C). The Investigator should ask the subject and/or the subject's parent/caregiver the following question: "Have you had any bleeding or bruising since I saw you last?". This assessment should be completed prior to other visit assessments.
- Collect blood for platelet count (local laboratory) and assess need for study drug dose titration per Table 3.
- Review study drug administration and Dosing Diary completion with the subject and/or the subject's caregiver.
- Record any AEs.
- Review and record any concomitant medications, including any modifications to concomitant ITP medications.
- Discharge subject from clinic with instructions for when to return for Visit 14.

9.1.15 Visit 14 (Core Phase - Week 12; Day 85 ± 1 Day)/Visit E-1 (Extension Phase)

For subjects who are continuing into the Extension Phase, Visit 14 will serve as the last visit in the Core Phase as well as the first visit in the Extension Phase (Visit E-1).

Procedures to Complete during Visit 14/Visit E-1 if the Subject is Continuing into the Open-label Extension Phase:

- Collect signed and dated informed consent/assent for the Extension Phase prior to any study procedures. The ICF/assent for the Extension Phase may be part of the ICF/assent for the Core Phase.
- Review of inclusion/exclusion criteria (Section 6.2) to confirm continued study eligibility.
- Perform WHO Bleeding Scale Assessment (Appendix C). The Investigator should ask the subject and/or the subject's parent/caregiver the following question: "Have you had any bleeding or bruising since I saw you last?". This assessment should be completed prior to other visit assessments.
- Collect height and weight to determine BMI (calculated by eCRF).
- Perform abbreviated PE. The abbreviated PE will consist of the following: general appearance, head, neck, eyes, ears, nose, throat, chest, lungs, heart, abdomen, extremities, joints, lymph nodes, and neurology.
- Collect vital signs (blood pressure, heart rate, and temperature). Vital signs should be taken after sitting for 5 minutes, whenever possible, and prior to any blood draws.
- Perform urine or serum pregnancy test for female subjects of childbearing potential. The pregnancy test may be performed locally.
- Collect blood for clinical laboratory tests (e.g., serum chemistry, hematology [Table 7]).

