- Collect blood for platelet count (local laboratory).
- Determine appropriate Extension Phase starting dose of open-label avatrombopag per the instructions in Section 1.1.6.

- Retrieve unused study drug from the Core Phase and record compliance in the eCRF.
- Dispense new Dosing Diary for the subject to take home with instructions for completion.
- Dispense 1-month supply of open-label avatrombopag for the subject to take at-home with instructions for administration.
- Review study drug administration and Dosing Diary completion with the subject and/or the subject's caregiver.
- Record any AEs.
- Review and record any concomitant medications, including any modifications to or new concomitant ITP medications.
- Discharge subject from clinic with instructions for when to return for Visit E-2/Month 2 (Section 9.1.19).

For subjects who are not continuing into the Extension Phase, Visit 14 should be completed and Visit 15 (Section 9.1.16) will be the last study visit.

Procedures to Complete during Visit 14/Visit E-1 if the Subject is NOT Continuing into the Open-label Extension Phase:

- Perform WHO Bleeding Scale Assessment (Appendix C). The Investigator should ask the subject and/or the subject's parent/caregiver the following question: "Have you had any bleeding or bruising since I saw you last?". This assessment should be completed prior to other visit assessments.
- Perform abbreviated PE. The abbreviated PE will consist of the following: general appearance, head, neck, eyes, ears, nose, throat, chest, lungs, heart, abdomen, extremities, joints, lymph nodes, and neurology.
- Collect height and weight to determine BMI (calculated by eCRF).
- Collect vital signs (blood pressure, heart rate, and temperature). Vital signs should be taken after sitting for 5 minutes, whenever possible, and prior to any blood draws.
- Collect blood for clinical laboratory tests (e.g., serum chemistry, hematology [Table 7]).
- Collect blood for platelet count (local laboratory).
- Perform urine or serum pregnancy test for female subjects of childbearing potential. The pregnancy test may be performed locally.
- Retrieve unused study drug and record compliance in the eCRF.
- Record any AEs.
- Review and record any concomitant medications, including any modifications to or new concomitant ITP medications.
- Discharge subject from clinic with instructions for when to return for Visit 15.

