Period	Screening ^a						Т	`reatmer	nt						End of Study/ Early Termination ^b
Visit	1	2 Baseline	3	4	5	6	7	8	9	10	11	12	13	14 ^c	Visit 15
Day	-28 to -1	1	8±1	15±1	22±1	29±1	36±1	43±1	50±1	57±1	64±1	71±1	78±1	85±1	30 Days (±7 days) after the last dose of study drug
Week (# is the End of Week)	-4	/	1	2	3	4	5	6	7	8	9	10	11	12	/
Vital Signs ^m	X	Xn	X	Xº	X	X		X		X		Xº		X	X
Serum Chemistry/Hematology (Central Lab)	X	X°				X				X				X	X
Platelet Count (Local Lab)	Xp	Xº	X	Xº	X	X	X	X	X	X	X	Xº	X	X	X
Assess need for Dose Titration				X	X	X	X	X	X	X	X	X	X	$X^{q,r}$	
Pregnancy Test ^s	X	X ^{o,t}				X				X				X	X
Plasma PK Sample(s) ^u			X	$X^{v,w}$	X	X	X	X	X	X	X	$X^{v,w}$			
Record Date/Time of Last Dose of Study Drug in eCRF			X	X	X	X	X	X	X	X	X	X			
Randomize Subject to Study Drug Arm		Xº													
Randomize Subjects in Cohort 3 to PK Timepoint		Xº													

m Vital signs (blood pressure, heart rate, and temperature) should be taken after sitting for 5 minutes, whenever possible. Vital signs should also be taken prior to any blood draws.

ⁿ Collect vital signs prior to study drug administration and 30 minutes (±15 minutes) after study drug administration.

^o Prior to dosing with study drug in clinic.

P The platelet count obtained at the Screening Visit/Visit 1 and 1 other platelet count taken within 28 days on either side of the Screening Visit (may use a historical value collected per standard of care if within 28 days of Screening) will be averaged to obtain the study eligibility platelet count value, which must be $<30\times10^9$ /L. The 2 samples must be obtained ≥24 hours and ≤28 days apart and the results must be available prior to randomization.

^q Only if subject is continuing into the open-label Extension Phase.

¹ If subject is continuing into the Extension Phase, determine appropriate starting dose based on protocol defined criteria.

^s Serum or urine pregnancy test should be performed for females of childbearing potential only.

^t Serum or urine pregnancy test should be performed prior to dosing with study drug.

^u Sparse blood sampling for the pharmacokinetic (PK) assessment will be performed, with the exception of Visit 4 (Week 2) and Visit 12 (Week 10) where serial PK samples will be taken.

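### Read literally, Section 1.5.4 gives a reduced Extension starting dose to a child above 250×10⁹/L, or still on hold after such a count, where Table 3 gives no drug until the count is ≤100

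*Protocol*

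**What the plan says.** Protocol Section 1.5.4 determines the Extension starting dose through three bullets, chosen by the platelet count at entry.

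- **50 to 150×10⁹/L on the current dose:** "they may continue that dose of open-label avatrombopag when entering the Extension Phase".
- **Below 50:** the Table 2 starting dose for the age cohort.
- **Above 150, no upper limit:** "the initial dose of open-label avatrombopag in the Extension Phase should be titrated down per the instructions in Table 4", based on the platelet count.

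Table 4 (Section 1.5.3) is a ladder of Levels 1 to 6. It contains no platelet thresholds and no zero-dose or hold level.

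Table 3 in the same section is titled "Study Drug Dose Adjustments in the Core Phase and Extension Phase". It divides the high range. From above 150 up to 250, the dose goes down one level. Above 250, drug is stopped, the site must "Increase platelet monitoring to twice weekly", and dosing moves one level down when the count is ≤100. A count above 250 after 2 weeks of once-weekly dosing means discontinuation.

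The visit lists cite Table 3 for titration through Visit 13 (Section 9.1.14): "Collect blood for platelet count (local laboratory) and assess need for study drug dose titration per Table 3". The Visit 14/E-1 list (Section 9.1.15) says instead: "Determine appropriate Extension Phase starting dose of open-label avatrombopag per the instructions in Section 1.1.6". Section 4.1.2 also refers to Section 1.1.6. The table of contents shows no such section; the text meant is evidently 1.5.4. The Table 7 footnote for Visit 14 reads "If subject is continuing into the Extension Phase, determine appropriate starting dose based on protocol defined criteria", and the matching row of Table 8 names no table.

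**The concern.** The rule that sets the first open-label dose and the protocol's high-count rule give different answers for the same child. One gives a lower active dose; the other gives no drug until the count has fallen to 100 or below. The subjects are children, and Section 10.2 makes thromboembolic events an adverse event of special interest for this drug. The surrounding instructions also point towards dosing. Table 8 and its footnote j mark in-clinic dosing at E-1, Section 9.1.15 has the site dispense a one-month supply, and neither makes an exception for a hold. The Extension entry criteria in Section 6.2 set no maximum platelet count.

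**Working it through.** No figure in the plan needs reproducing. The check sets the two rules side by side and works out the dose difference from Table 4.

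**Step 1. Compare the rules by entry count (×10⁹/L).**

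| Child at Visit 14/E-1 | Section 1.5.4, literal | Table 3 | Result |
|---|---|---|---|
| >150 to ≤250, no hold | reduced dose | down one level | agree |
| >250 | reduced dose | stop, wait for ≤100 | conflict |
| On a >250 hold, now >150 to ≤250 | reduced dose | still held | conflict |
| On a >250 hold, now >100 to ≤150 | first bullet; hold not mentioned | still held | gap |

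The last row does not come from the third bullet. The first bullet depends on a current dose, and a child on hold has none, so it is unclear whether the bullet applies.

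**Step 2. Weekly dose at each level of Table 4 (mg/week).**

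| Level | Tablet (Cohorts 1 and 2) | Capsule (Cohort 3) |
|---|---|---|
| 6 | 40×7 = 280 | 20×7 = 140 |
| 5 | 40×3 + 20×4 = 200 | 20×3 + 10×4 = 100 |
| 4 | 20×7 = 140 | 10×7 = 70 |
| 3 | 20×3 = 60 | 10×3 = 30 |
| 2 | 20×2 = 40 | 10×2 = 20 |
| 1 | 20 | 10 |

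The third bullet does not say how many levels to go down. The highest resulting dose is Level 6 to Level 5: 200 mg (tablet) or 100 mg (capsule). The lowest is any reduction to Level 1: 20 mg or 10 mg. A strict one-level step gives the same range, because Level 2 to Level 1 is also one step. From the usual starting level (Level 4), one step down gives 60 mg or 30 mg. From Level 1 there is nothing lower, so the bullet cannot be carried out. Table 3 gives 0 mg in each case until the count is ≤100. Cohort 3 escalations above Level 6 are left out.

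**Step 3. Monitoring in the first week.** Section 4.1.2 asks for weekly counts after E-1 until the dose is stable: 1 count. Table 3 above 250 asks for 2.

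**Step 4. Where Table 3 is cited.** Visits 4 to 13 cite it for titration (13 − 4 + 1 = 10 visits), as do E-2 to E-24 (24 − 2 + 1 = 23 visits), 33 in all. The Visit 14/E-1 list does not, and Section 1.5.4 never names Table 3.

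**The case against.** The best answer is that the protocol uses Table 4 as shorthand for Tables 3 and 4 together. The third bullet tells the site to go by the platelet count, and only Table 3 supplies counts. The closing dosing sentence of Section 1.5.4 uses the same Table 4 phrase for all Extension titration, while Section 9.2.3 says that titration at E-2 to E-24 follows Table 3. Sections 1.4.1, 1.5.3 and 4.1.1.2 cite Table 4 just as loosely. Table 3 covers the Extension by its title, nothing in 1.5.4 lifts a hold, and Tables 7 and 8 mark a titration assessment at Visit 14/E-1. On this view the fault is an imprecise cross-reference and the section number a clerical slip.

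Much of this stands: a careful site could well reach Table 3. It does not remove the literal conflict. At every other visit where titration is assessed, the procedure list corrects the loose wording by naming Table 3. At E-1 it does not, and a site that finds the right section still does not meet Table 3 there.

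It is also fair that the group is small. Visit 13 applies Table 3 a week earlier, so a child above 250 at E-1 has either crossed that line since then or is already under a stop order. Section 6.2.2 lets the investigator keep a child out for significant safety concerns. Table 3's discontinuation rule covers part of the Level 1 problem.

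**Conclusion.** The point holds as a defect of wording with a dosing-safety consequence. As written, the third bullet prescribes active drug in two situations where Table 3 prescribes none: a count above 250×10⁹/L at Visit 14/E-1, and a hold in progress with the count still above 150. The difference in the first week is 20 to 200 mg against 0 mg for tablets, or 10 to 100 mg against 0 mg for capsules, with one count instead of two.

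This assumes a site that follows Section 1.5.4 to the letter, and that Table 3's restart condition means no drug until ≤100. The documents do not say how many children would be affected; the number should be small. Weekly counts after E-1 should expose an error in about a week. Core Phase efficacy, sample size, power and alpha are unaffected. It should be fixed because the conflict concerns dosing in children and is easily removed.

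**What to change.** - Limit the third bullet of Section 1.5.4 to counts above 150 and up to 250×10⁹/L, with a decrease of one level under Tables 3 and 4.
- Add that a count above 250 at entry, or any Table 3 hold in progress whatever the current count, follows Table 3: no E-1 dose, twice-weekly counts, open-label drug started one level lower at ≤100, and discontinuation if above 250 after 2 weeks of once-weekly dosing.
- Make dosing and dispensing at E-1 conditional on this in Section 9.1.15 and Table 8, footnote j.
- Cite Table 3 in Sections 1.5.4 and 9.1.15, and change the Section 1.1.6 references in Sections 4.1.2 and 9.1.15 to 1.5.4.

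The cost is a wording amendment. The only downside is a short delay in open-label dosing for children whom Table 3 already says should not be dosed.

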2 STUDY OBJECTIVES

2.1 Primary Objective

To demonstrate that the efficacy of avatrombopag is superior to placebo for the treatment of pediatric subjects with ITP of ≥ 6 months duration who have had an insufficient response to a previous treatment.

2.2 Secondary Objectives

- To evaluate the safety and tolerability of avatrombopag
- To evaluate the PK and PD of avatrombopag

2.3 Exploratory Objective

To provide data on the palatability and parent/caregiver reported acceptability of the avatrombopag powder for oral suspension.

3 STUDY ENDPOINTS

In order to satisfy the primary endpoint requirements of different regulatory agencies, 2 separate SAPs will be developed for this study. In the first SAP, the endpoint described as "Primary Efficacy Endpoint" in Section 3.1 will be assessed as the primary efficacy endpoint, and the endpoint described as the "Alternative Primary Efficacy Endpoint" in Section 3.2 will be assessed as the first secondary efficacy endpoint. In the second SAP, the endpoint described as "Alternative Primary Efficacy Endpoint" in Section 3.2 will be assessed as the primary efficacy endpoint, and the endpoint described as the "Primary Efficacy Endpoint" in Section 3.1 will be assessed as the first secondary efficacy endpoint. Both SAPs will evaluate the additional secondary efficacy endpoints described in Section 3.3.

3.1 Primary Efficacy Endpoint

Durable platelet response as defined by the proportion of subjects achieving at least 6 out of 8 weekly platelet counts $\geq 50 \times 10^9$ /L during the last 8 weeks of the 12 week Treatment Period in the Core Phase in the absence of rescue medication.

3.2 Alternative Primary Efficacy Endpoint

Platelet response as defined by the proportion of subjects for whom at least 2 consecutive platelet assessments are $\geq 50 \times 10^9 / L$ over the 12 week Treatment Period in the Core Phase in the absence of rescue medication.

3.3 Additional Secondary Efficacy Endpoints

- The percentage of weeks subjects have a platelet count $\geq 50 \times 10^9 / L$ during 12 weeks of treatment in the Core Phase, in the absence of rescue therapy.
- Platelet response at Day 8 (defined by the proportion of subjects with a platelet count $\geq 50 \times 10^9 / L$ at Day 8, in the absence of rescue therapy).

- The percentage of weeks subjects have a platelet count between $\geq 50 \times 10^9 / L$ and $\leq 150 \times 10^9 / L$, during 12 weeks of treatment in the Core Phase, in the absence of rescue therapy.
- The proportion of subjects who require rescue medications during 12 weeks of treatment in the Core Phase of the study.
- Incidence and severity of bleeding symptoms associated with ITP measured using the WHO Bleeding Scale.

3.4 Safety Endpoints

- Incidence of AEs, SAEs, and AEs of special interest (AESI) during the study.
- Measurement of clinical laboratory tests during the study.
- Measurement of vital signs during the study.

3.5 Pharmacokinetic and Pharmacodynamic Endpoints

- Individual PK parameters will be derived from the final population PK model. Effects of intrinsic factors, including age and weight, and extrinsic factors, including formulation, on the PK parameters may be evaluated.
- Effects of covariates on PD parameters may be evaluated.

